10.2.3 Treatment-Emergent Adverse Events by SOC and/or PT

The following summary of treatment-emergent adverse events will be summarized by SOC and PT:

- All TEAE
- Serious TEAEs
- Severe TEAEs
- TEAEs related to study drug according to the investigator
- TEAEs leading to discontinuation of study drug
- TEAE leading to death

- COVID-19 related TEAE

TEAE will also be summarized by maximum relationship to study drug as assessed by the investigator (e.g., reasonable possibility or no reasonable possibility) and SOC and PT; by maximum severity and SOC and PT; and by subject number and SOC and PT. Specific adverse events will be counted once for each subject for calculating percentages, unless stated otherwise. In addition, if the same adverse event occurs multiple times within a subject, the highest severity and level of relationship to investigational product will be reported.

In addition, treatment-emergent adverse events will be summarized by PT and sorted by decreasing frequency for the total active group.

10.2.4 Treatment-Emergent Adverse Events per Patient-Years of Exposure

For SA2 and SA2_P2 populations, an overview of AEs per 100 patient-years of study exposure and an overview of ASI per 100 patient-years of study exposure will be presented.

Exposure-adjusted AEs per 100 patient-years will be provided for SA2_ALL for the following categories:

- AE overview
- ASI overview
- All TEAEs by SOC and PT
- All serious TEAEs by SOC and PT
- All Severe TEAEs by SOC and PT
- TEAEs related to study drug according to the investigator by SOC and PT
- TEAEs leading to discontinuation of study drug by SOC and PT
- TEAE leading to death by SOC and PT
- COVID-19 related TEAE by SOC and PT

- TEAE by PT and sorted by decreasing frequency for the total active group
- SAEs (including deaths) and AEs leading to study drug discontinuation by SOC and PT and in listing format.
- ASI by SOC and PT (or by Adjudicated Terms)

Calculation of EAER is defined in Section 10.2.

10.2.5 SAEs (Including Deaths) and Adverse Events Leading to Study Drug Discontinuation

SAEs (including deaths) and AEs leading to study drug discontinuation will be summarized by SOC and PT and in listing format. Calculation of EAER is defined in Section 10.2.

10.2.6 Areas of Safety Interest

Areas of Safety Interest will be summarized by SOC and PT and will be based on standardized or company MedDRA queries (SMQs or CMQs). Adjudicated cardiovascular events will be summarized and presented by treatment group using the CAC adjudicated categories. Areas of Safety Interest are categorized as follows:

- Adjudicated MACE
- Adjudicated extended MACE
- Serious infections
- Active Tuberculosis
- Opportunistic infections excluding tuberculosis and herpes zoster
- Herpes zoster
- Malignancies (Malignant tumours, NMSC and Malignancies excluding NMSC)
- Hypersensitivity
- Serious hypersensitivity
- Adjudicated Anaphylactic reactions
- Hepatic events

- Injection site reactions

Detailed information about the search criteria is provided in [Appendix C](#).

In addition, an overview of ASI per 100 patient-years of study exposure will be presented. The number of TEAEs reported, the total number of years of study drug exposure, and the TEAE rate per 100 patient-years will be presented.

The exposure adjusted incidence rate (censored at the time of first event) may be conducted for deaths and selected Areas of Safety Interest categories including adjudicated cardiovascular events, malignant tumors, non-melanoma skin cancer (NMSC), and malignant tumors excluding NMSC, as appropriate.

Tabular listings of ASI listed above will also be provided.

10.3 Analysis of Laboratory Data

Data collected from central and local laboratories, including additional laboratory testing due to an SAE, will be used in all analyses, except for Baseline where SAE-related laboratory assessments on or before the first dose of study drug will be excluded. The clinical laboratory tests defined in the protocol (e.g., hematology and clinical chemistry) will be summarized.

Analysis of Quantitative Laboratory Parameters

For SA2 and SA2_P2 populations, each laboratory variable will be summarized for all time points (starting with Baseline) with the number of non-missing observations, mean and standard deviation, median, minimum and maximum. Mean change from baseline to each applicable post-baseline visit will be summarized for selected laboratory variables, with the number of observations, baseline mean, and visit mean. The change from baseline mean, standard error, and 95% confidence interval will be presented for the mean change from baseline within each treatment group. In addition, for SA2_P2 populations, each laboratory variable will be summarized for all time points (starting with Induction

Period 2 baseline referring to the last available measurement before first dose in Induction Period 2) with the number of non-missing observations, mean and standard deviation, median, minimum and maximum. Mean change from Induction Period 2 baseline to each applicable post-baseline visit will be summarized for selected laboratory variables, with the number of observations, baseline mean, and visit mean. The change from Induction Period 2 baseline mean, standard error, and 95% confidence interval will be presented for the mean change from Induction Period 2 baseline within each treatment group.

For SA2 population, treatment group differences between Risankizumab 1200 mg IV treatment group and placebo group for changes from Baseline will be analyzed using a one-way Analysis of Variance (ANOVA) model with treatment as a fixed factor and 95% CI for treatment difference will be presented for selected laboratory parameters.

Shift Table Analyses

For SA2 and SA2_P2 populations, changes in laboratory parameters will be tabulated using shift tables either by NCI CTC criteria or categorized as low, normal, or high based on the normal ranges of the laboratory used for each sample. A shift table from baseline either to the worse value (based on NCI CTC criteria) during treatment or to minimum and maximum value (based on normal range), will be created. A similar shift table will be provided to summarize shifts from baseline to the final post-baseline value.

Potentially Clinically Significant Laboratory Values

For SA2, SA2_P2 and SA2_ALL populations, laboratory abnormalities meeting CTC criteria grade 3, grade 4 and \geq Grade 3 will be summarized, with a grade worsening compared to baseline.

Laboratory abnormalities will be evaluated based on Potentially Clinically Significant (PCS) criteria (). For each laboratory PCS criterion, the number and percentage of subjects who have a laboratory value meeting the criteria will be summarized. Listings will be provided to summarize subject-level laboratory data for subjects meeting PCS criteria.

Assessment of Liver Elevations

For SA2, SA2_P2 and SA2_ALL populations, the liver-specific laboratory tests include the serum glutamic pyruvic transaminase (SGPT/ALT), serum glutamic-oxaloacetic transaminase (SGOT/AST), alkaline phosphatase (ALP), and total bilirubin (TBL). The frequencies and percentages of subjects with post baseline liver specific function test values that meet the following criteria of potential clinical interest will be summarized by treatment group:

- $ALT \geq 3 \times ULN$
- $ALT \geq 5 \times ULN$
- $ALT \geq 10 \times ULN$
- $ALT \geq 20 \times ULN$
- $AST \geq 3 \times ULN$
- $AST \geq 5 \times ULN$
- $AST \geq 10 \times ULN$
- $AST \geq 20 \times ULN$
- $TBL \geq 2 \times ULN$
- $Alkaline\ phosphatase \geq 1.5 \times ULN$
- $(ALT\ and/or\ AST \geq 3 \times ULN)\ and\ (TBL \geq 1.5 \times ULN)$
- $(ALT\ and/or\ AST \geq 3 \times ULN)\ and\ (TBL \geq 2 \times ULN)$

where ULN is the upper limit of normal.

A listing of potentially clinically significant liver function laboratory values will be provided. The listing will include all subjects who met any of the following 4 criteria:

- $ALT \geq 3 \times ULN$, or
- $AST \geq 3 \times ULN$, or
- $Alkaline\ phosphatase \geq 1.5 \times ULN$, or
- $Total\ bilirubin \geq 1.5 \times ULN$.

A listing of possible Hy's Law cases, defined as those who meet all of the following conditions at any post-baseline visit will be provided:

- ALT of $> 3 \times \text{ULN}$ or AST of $> 3 \times \text{ULN}$,
- Total bilirubin $\geq 2 \times \text{ULN}$.

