Changes from Baseline in continuous laboratory and vital sign parameters will be summarized by treatment group for corresponding safety population in each sub-study. Treatment group differences in changes from Baseline between risankizumab and the placebo group may be analyzed using a one-way Analysis of Variance (ANOVA). Vital signs and laboratory data will be summarized by descriptive statistics and frequency of abnormal values. In addition, shift tables and listings will be provided for abnormal values, whereby the normal range of the analyzing laboratory will be used.

Missing safety data will not be imputed. More detailed safety analysis for Induction Period 1 and Induction Period 2 will be specified in SAP.

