2.2 Study Design Overview

Study M16-067 Sub-Study 2 is a Phase 3, multicenter, randomized, double-blind, placebo-controlled study designed to evaluate the efficacy and safety of risankizumab as

induction therapy in adult subjects with moderately to severely active UC, defined as Adapted Mayo score of 5 – 9 points (using the Mayo scoring system, excluding Physician's Global Assessment) with an endoscopic subscore of 2 or 3 on screening endoscopy, confirmed by central review.

Sub-Study 2 will enroll subjects who have had an intolerance or inadequate response (IR) to prior biologic therapy (bio-IR) and subjects who have not had an intolerance or inadequate response to prior biologic therapy (non-bio-IR). The bio-IR enrollment in Sub-Study 2 will be approximately 541 subjects and the non-bio-IR enrollment will be approximately 425 subjects.

The bio-IR population is defined as subjects with documented intolerance or inadequate response to one or more of the approved biologics for UC (infliximab, adalimumab, golimumab, and/or vedolizumab) or tofacitinib. The non-bio-IR population will include subjects who had an inadequate response or intolerance to conventional therapy.

Conventional therapy is defined as one or more of the following: aminosalicylates, oral locally acting steroids (e.g., budesonide, beclomethasone), systemic corticosteroids (prednisone or equivalent), or immunomodulators. This population will also include subjects who have received biologic therapy or tofacitinib in the past but stopped therapy based on reasons other than inadequate response or intolerance (e.g., change in reimbursement coverage, well-controlled disease).

The study duration may be up to 45 weeks, including a Screening period of approximately 35 days, a 12-week Induction Period 1, a 12-week Induction Period 2 for those subjects who do not achieve clinical response at Week 12, and a 140-day follow-up period from the last dose of study drug.

[figure not shown]
Sub-Study 2 Induction Period 1:

Subjects (n = 966) who meet all of the inclusion criteria and none of the exclusion criteria will be enrolled into the double-blind 12-week study and randomized in a 2:1 ratio to one of the following treatment groups:

- Group 1: Risankizumab 1200 mg IV Weeks 0, 4, 8 (n = 644)
- Group 2: Placebo IV Weeks 0, 4, 8 (n = 322)

The schematic of the Induction Period 1 is shown in [Figure 1](#).

Figure 1. Study Schematic of Induction Period 1

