- ANCOVA: For continuous efficacy variables that are collected at only one post-baseline visit, ANCOVA will be used. The model includes the categorical fixed effects of treatment, stratification factors, and the continuous fixed covariates of baseline and measurement.

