10.0 Safety Analyses

10.1 General Considerations

Safety analysis will be performed on the safety populations in Induction Period 1 (SA2 population) and Induction Period 2 (SA2_P2 population) in Sub-Study 2. Safety summaries will be presented by treatment group, including a total group for all subjects on active study drug for SA2_P2. In addition, safety analysis will be provided for all Risankizumab treated safety population (SA2_ALL population) combined as one group.

For the safety analysis, subjects are assigned to a treatment group based on the treatment actually received, regardless of the treatment randomized.

The standard safety analyses will include reporting of adverse events (AEs), Areas of Safety Interest (ASIs), laboratory, and vital signs measurements. Frequency tables of subjects with treatment-emergent adverse events (TEAEs) by system organ class (SOC) and by preferred term (PT) as in the Medical Dictionary for Regulatory Activities (MedDRA) dictionary will be provided by treatment group. All continuous laboratory parameters and vital signs variables at each visit will also be summarized by actual treatment group. Frequency tables of subjects meeting criteria for potentially clinically significant vital sign values and for potentially clinically significant laboratory values will be provided by treatment group.

Missing safety data will not be imputed.

Baseline for laboratory and vital signs

For SA2 population, the baseline value is defined as the last available measurement before study drug administration for each subject. For SA2_P2 and SA2_ALL populations, the baseline value is defined as the last available measurement on or before first dose of risankizumab.

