10.4 Analysis of Vital Signs

Vital sign measurements of systolic and diastolic blood pressure, pulse rate, body weight and body temperature will be summarized.

For SA2 and SA2_P2 populations, each vital sign variable will be summarized for all time points (starting with Baseline) with the number of non-missing observations, mean and standard deviation, median, minimum and maximum. Mean change from baseline to each applicable post-baseline visit will be summarized for each vital sign variable, with the number of observations, baseline mean, and visit mean. The change from baseline mean, standard error, and 95% confidence interval will be presented for the mean change from baseline within each treatment group. In addition, for SA2_P2 populations, each vital sign variable will be summarized for all time points (starting with Induction Period 2 baseline referring to the last available measurement before first dose in Induction Period 2) with the number of non-missing observations, mean and standard deviation, median, minimum and maximum. Mean change from Induction Period 2 baseline to each applicable post-baseline visit will be summarized for selected laboratory variables, with the number of observations, baseline mean, and visit mean. The change from Induction Period 2 baseline mean, standard error, and 95% confidence interval will be presented for the mean change from Induction Period 2 baseline within each treatment group.

For SA2 population, treatment group differences between Risankizumab 1200 mg IV treatment group and placebo group for changes from Baseline will be analyzed using a one-way Analysis of Variance (ANOVA) with treatment as a fixed factor and 95% CI for treatment difference will be presented for each vital sign variable.

For SA2, SA2_P2 and SA2_ALL populations, vital sign variables will be evaluated based on potentially clinically significant (PCS) criteria (). For each vital sign PCS criterion, the number and percentage of subjects who have a vital sign value meeting the criteria will be summarized. Listings will be provided to summarize subject-level vital sign data for subjects meeting PCS criteria.

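### Laboratory and vital-sign changes are compared by one-way ANOVA without a baseline covariate: valid, but less precise than the same data allow

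*SAP*

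**What the plan says.** For the SA2 population, SAP 10.3 analyses laboratory changes from Baseline, risankizumab 1200 mg IV against placebo. The method is the "one-way Analysis of Variance (ANOVA) model with treatment as a fixed factor", reported with a 95% CI on the difference for a selection of parameters. SAP 10.4 repeats the model for vital signs: "one-way Analysis of Variance (ANOVA) with treatment as a fixed factor and 95% CI for treatment difference will be presented for each vital sign variable". Treatment is the only term in either model.

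The protocol agrees on the method. The safety paragraph of its synopsis names one-way ANOVA for laboratory changes and says that vital signs are handled similarly. Protocol 8.1.7 names the same ANOVA but in permissive wording.

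The covariate exists. SAP 10.1 states: "For SA2 population, the baseline value is defined as the last available measurement before study drug administration for each subject". A subject must have that value to have a change score at all.

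Elsewhere the SAP does adjust. Under SAP 9.2.2 the MMRM carries the baseline measurement as a covariate, and for ANCOVA "The model includes the categorical fixed effects of treatment, stratification factors, and the continuous fixed covariates of baseline and measurement" (the last words evidently mean the baseline measurement). SAP 10.5 and 10.6 plan no further safety analysis, so no baseline-adjusted comparison of laboratory or vital-sign data is planned anywhere.

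**The concern.** Subtracting baseline is not the same as adjusting for it. ANOVA on change fixes the slope of follow-up on baseline at 1. With equal SDs the actual slope is rho, which is below 1 for any measure that varies within a subject. Two things follow. The change score carries noise that a fitted slope would remove, so the interval is wider than it needs to be. And if one arm happens to start higher, regression to the mean pulls that arm down more, and part of the chance imbalance stays in the estimated treatment difference.

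At stake is the sharpness of the between-arm mean differences and 95% CIs that the SAP says it will present for selected laboratory parameters and for every vital sign. In a safety comparison, a wider interval makes a modest real shift harder to tell from none.

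**Working it through.** **Plan's own figure.** There is none to reproduce. The documents give no SD, correlation, interval width or power for any laboratory or vital-sign comparison.

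**Inputs.** Planned arm sizes 644 and 322 (SAP 2.2). Assumptions, not in the documents: correlation rho between baseline and follow-up, taken from 0.3 to 0.9; equal SD s at both times; one slope common to both arms.

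**Formulas.**
- Arm-size factor: k = sqrt(1/644 + 1/322) = 0.0683. This is also the SD of the chance baseline difference between arms, in baseline SDs.
- ANOVA on change: variance 2s²(1-rho); 95% half-width 1.96 × s × sqrt(2(1-rho)) × k.
- Baseline-adjusted: variance s²(1-rho²); 95% half-width 1.96 × s × sqrt(1-rho²) × k.
- Variance ratio, adjusted to unadjusted: (1-rho²) / [2(1-rho)] = (1+rho)/2. Excess width of the planned interval: sqrt(2/(1+rho)) - 1, which does not depend on the arm sizes.
- Given a baseline difference D, the ANOVA estimate shifts by -(1-rho)D and the adjusted estimate by 0.

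**Worked case, rho = 0.5.** Planned: 1.96 × 1 × 0.0683 = 0.134 SD. Adjusted: 1.96 × 0.866 × 0.0683 = 0.116 SD. Excess: sqrt(2/1.5) - 1 = 15.5%. An imbalance at its 1.96-SD limit is 1.96 × 0.0683 = 0.134 SD, and it moves the ANOVA estimate by 0.5 × 0.134 = 0.067 SD.

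| rho | Variance ratio | Planned half-width (SD) | Adjusted half-width (SD) | Planned wider by | Size of shift at 1.96-SD imbalance (SD) |
|---|---|---|---|---|---|
| 0.3 | 0.65 | 0.158 | 0.128 | 24.0% | 0.094 |
| 0.5 | 0.75 | 0.134 | 0.116 | 15.5% | 0.067 |
| 0.7 | 0.85 | 0.104 | 0.096 | 8.5% | 0.040 |
| 0.8 | 0.90 | 0.085 | 0.080 | 5.4% | 0.027 |
| 0.9 | 0.95 | 0.060 | 0.058 | 2.6% | 0.013 |

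**Unequal SDs.** Let q be the follow-up SD divided by the baseline SD. In baseline SDs, the planned analysis works with sqrt(1 + q² - 2 × rho × q) and the adjusted one with q × sqrt(1-rho²). At rho 0.5 the excess is 32.3% for q = 0.8 (0.917 against 0.693) and 5.8% for q = 1.25 (1.146 against 1.083). At rho 0.7 it is 26.2% and 1.0%. The two analyses are equally precise only when the slope rho × q equals 1.

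**Simulation check.** 4,000 trials were run at 644:322 for each of rho 0.5 and 0.7, with equal SDs and no treatment effect. The ratio of standard errors, ANOVA to ANCOVA, was 1.146 and 1.079 (formula: 1.155 and 1.085). The slope of the estimate on the baseline imbalance was -0.48 and -0.29 for ANOVA (formula: -0.5 and -0.3), against 0.02 and 0.01 for ANCOVA. Both estimates averaged about 0.

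**The case against.** The strongest reply is that nothing here is an error. ANOVA on change is a valid randomised comparison and already uses the baseline by subtraction. No decision rests on it: SAP 13.0 confines type I error control to the primary and secondary efficacy endpoints, and SAP 10.3 and 10.4 set no margin or decision rule. Individual-level signals are picked up by shift tables, Grade 3 or higher abnormalities with grade worsening, potentially clinically significant criteria and the liver tables, none of which uses this model. Baseline and visit means are displayed too, so an imbalance would be visible. In absolute terms the half-width falls by only 0.008 SD at rho 0.7 (0.104 - 0.096) and 0.018 SD at rho 0.5 (0.134 - 0.116).

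All of that stands, and it sets the severity. It does not make the covariate a mere matter of taste, because the SAP commits to presenting these intervals and can have narrower ones from the same subjects.

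A second reservation also stands in part. With 2:1 allocation and slopes that differ strongly between arms, the gain from a common-slope ANCOVA could shrink. The figures above assume a common slope.

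A reader might infer that the planned safety differences are biased, that their intervals are invalid, or that a chance imbalance passes in full into the estimate. The documents and the check do not support any of these. The estimate averages to the true difference over randomisation, and only the fraction (1-rho) of an imbalance remains, with opposite sign. Nor is a 10 to 35% cut in variance a property of this trial: it is (1+rho)/2 evaluated at assumed correlations from 0.8 down to 0.3 with equal SDs.

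**Conclusion.** The point holds as a minor efficiency point. The planned comparisons are unbiased over randomisation with valid 95% CIs, but they leave out a covariate that every analysed subject has and that the SAP uses for its continuous efficacy endpoints. With equal SDs and a common slope, the cost runs from about 24% extra interval width for a noisy measure (rho 0.3) to 2.6% for a very stable one (rho 0.9). It varies further with the SD ratio. Correlation, SDs and common slope are all assumptions, so the size for any particular parameter is unknown until its data are seen. No primary or secondary efficacy conclusion changes, and the shift, potentially-clinically-significant and liver tables are unaffected.

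**What to change.** In SAP 10.3 and 10.4, replace the one-way ANOVA with an ANCOVA on change from Baseline, with treatment as a fixed factor and the baseline value of the same parameter as a continuous covariate. Report the adjusted difference with its 95% CI. Settle this before unblinding, so that the model is not chosen after the results are seen.

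The protocol names the one-way ANOVA in the synopsis safety paragraph, in firm wording, and in 8.1.7, in permissive wording. Either align both places or record the difference in the SAP. SAP 1.0 already says that changes from the protocol analyses are outlined in SAP 14.0, so an entry there would do.

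The cost is one model term, two short SAP edits and the protocol alignment or version-history entry. It needs no new data, loses no subjects who have a change score, and does not touch the multiplicity plan.
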